In case of  $C_{0h}$ , observed pre-dose exposure may be used as an alternative to the model-estimated  $C_{0h}$ .

The drug effect sub-model may be parametrized as a linear, or if the exposure range allows,  $E_{max}$ , sigmoid  $E_{max}$ , or exponential function, as determined by model building criteria (Section 4.9). In case a delay in onset of drug effect will be observed during the exploratory analysis, the delay will be fit using an appropriate delay function, such as a sigmoid. Additional functional forms of the drug effect sub-models may be tested. Baseline MADRS or SHAPS will be tested as covariate on both drug-related and drug-non-related response in order to assess the potential influence of higher/lower baseline disease severity on MADRS and SHAPS change. Gender, race, and age at baseline will also be tested. Lead-in placebo response will be tested as covariate on models based on the full dataset for change from baseline MADRS scores. Lead-in placebo response will not be tested as covariate for change from baseline SHAPS models, as no effect was observed on SHAPS during the lead-in period based on blinded data. Additional parameter-covariate relationships may be tested if required.

Primary analysis on MADRS will be performed on the enriched population (lead-in non-responders). In case no effect on MADRS is found, change from baseline SHAPS total scores will be analyzed on the full dataset. If appropriate, the analysis on MADRS may be repeated on the full dataset, where both lead-in placebo response as well as baseline SHAPS total score will be tested as covariate in the model.

Change from baseline MADRS or SHAPS total scores obtained during the withdrawal period (Day 78) may be explored and included in the model as function of exposure if deemed appropriate.

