#### 4.7. Simulations

Based on the final PK/PD model (including covariates, if any), model-based simulations of placebo corrected change from baseline in MADRS/SHAPS will be generated. The following simulations will be performed:

- a) Population distribution of the MADRS and SHAPS change from baseline and of the drug effect on MADRS and SHAPS at Week 6 vs AUC;
- b) Probability to achieve a drug effect on MADRS and SHAPS of at least 1, 2, or 3 points drop at Week 6 in the population;
- c) Point estimate and 90% confidence interval (CI) for the MADRS and SHAPS change from baseline and for the drug effect on MADRS and SHAPS at Week 6 vs AUC for the population studied;
- d) Model-based MADRS and SHAPS change from baseline vs time by lead-in placebo-response.

Simulations (a), (b) and (d) will be performed using 10,000 subjects per dose level in order to adequately reflect PK and PD variability in a large population. For this purpose, interindividual variability in PK and in PD parameters, as well as residual variability in MADRS and SHAPS, will be included in the simulations. Uncertainty of model parameter estimates will not be included. Simulations will be performed at the 10 mg qd dose level. Other dosing regimen may be included if deemed appropriate. The simulations will be summarized as median, 5th and 95th percentiles of the population. Simulations (a), (b) and (c) may be repeated for additional treatment days of

interest. When appropriate, simulations will be performed in sub-populations based on specific selection criteria, such as lead-in-placebo-response or baseline SHAPS scores.

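### SAP 4.7(d) requires simulated curves by lead-in response, but SAP 4.6 does not secure a SHAPS or MADRS model that supports the split

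*SAP*

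**What the plan says.** SAP 4.7 takes its simulations from whatever model emerges from 4.6: "Based on the final PK/PD model (including covariates, if any), model-based simulations of placebo corrected change from baseline in MADRS/SHAPS will be generated". Item (d) of its list is "Model-based MADRS and SHAPS change from baseline vs time by lead-in placebo-response". Unlike the separate sub-population simulations, (d) carries no condition of its own.

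SAP 4.6 then sets the models:

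- **SHAPS.** "Lead-in placebo response will not be tested as covariate for change from baseline SHAPS models, as no effect was observed on SHAPS". The full reason is that "no effect was observed on SHAPS during the lead-in period based on blinded data". The SHAPS analysis is placed on the full dataset if no MADRS effect is found, so responders and non-responders are both in that model.
- **MADRS, primary.** "Primary analysis on MADRS will be performed on the enriched population (lead-in non-responders").
- **MADRS, further.** "If appropriate, the analysis on MADRS may be repeated on the full dataset, where both lead-in placebo response as well as baseline SHAPS total score" are to be tested as covariates. A companion sentence confirms it: "Lead-in placebo response will be tested as covariate on models based on the full dataset for change from baseline MADRS scores". The refit itself remains discretionary.

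Baseline score is tested as a covariate on both the drug and non-drug parts of the response, and an open clause allows further covariate relationships. All of this modelling happens only if the exploratory plots suggest an exposure-efficacy relationship.

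**The concern.** Item (d) asks for a comparison between two groups. For SHAPS, the model behind it will not estimate a difference between those groups. For MADRS, the primary model has seen only one of them.

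The reason given for leaving lead-in response out of the SHAPS model concerns the weeks when everyone was on placebo. It does not show that, after randomisation, SHAPS follows the same course in MADRS lead-in responders and non-responders, or that the drug acts on it equally. SAP 3.1 also excludes lead-in data from this analysis, so the evidence cited lies outside the modelled period.

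Lead-in status is not a minor variable elsewhere in the plan. Randomisation is stratified by it (protocol 6.3), missing baseline MADRS and SHAPS are imputed within it (SAP 3.2.2), and the exploratory SHAPS plots are split by it (SAP 4.2 and 4.6).

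At stake is how (d) is read. It is simulated with 10,000 subjects per dose level and leaves out parameter uncertainty (SAP 4.7). Smooth, similar SHAPS curves by lead-in group could pass for a result when the similarity came mostly from the model's form.

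**Working it through.** **1. What the SHAPS model can show.** In the SAP 4.6 equation, the placebo parameters for the five post-baseline visits are common to all subjects, the subject effect has mean zero, and the drug effect depends on visit and exposure. With no lead-in term, the expected difference between lead-in groups is

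difference = sum over retained covariates of (slope × group difference in that covariate), plus any exposure difference.

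An illustration with assumed values (not from the documents): Week 6 placebo change −4.5, drug effect −2, covariate centred at 34, mean baseline 35 in non-responders and 31 in responders.

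| Baseline slope | Expected, non-responders | Expected, responders | Simulated medians (10,000 per group) |
|---|---|---|---|
| 0 | −4.5 − 2 = −6.5 | −6.5 | −6.4 and −6.6 |
| −0.3 | −6.5 − 0.3 × 1 = −6.8 | −6.5 + 0.3 × 3 = −5.6 | −6.8 and −5.7 |

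The curves can separate, but only by what baseline score carries (0.3 × 4 = 1.2 points here). A difference due to lead-in status itself cannot appear.

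**2. What the MADRS models can show.** The primary model has no responders, so nothing in it informs a responder curve. The full-dataset refit would have both groups and would test lead-in response. It is optional while (d) is not, and no rule covers (d) if the term is tested and then dropped.

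**3. How many responders to expect.** Protocol 9.1 gives 96 to be randomised, 25% lead-in response and 10% lead-in drop-out. Its figure reproduces: 96 / (0.75 × 0.90) = 142.2, stated as 142. Forward from 142:

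- randomised: 142 × 0.90 = 127.8, about 128
- non-responders: 127.8 × 0.75 = 95.9, about 96 (48 per arm)
- responders: 127.8 × 0.25 = 32.0, about 32 (16 per arm)

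**4. What the data could say about SHAPS by stratum.** The documents give no SD for SHAPS change, so 6 to 8 points is an assumption. These are simple-contrast standard errors at one visit.

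| Contrast | Formula | SE at SD 6 | SE at SD 8 |
|---|---|---|---|
| Placebo arm, responders vs non-responders | SD × √(1/16 + 1/48) = 0.289 × SD | 1.7 | 2.3 |
| Difference in drug effect between strata | SD × √(2/16 + 2/48) = 0.408 × SD | 2.4 | 3.3 |

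A 4-point difference, chosen only for scale, is 4/1.7 to 4/2.3, or about 2.3 to 1.7 standard errors in the placebo arm. For the drug effect it is about 1.6 to 1.2. A shift in the placebo course is therefore estimable with modest precision, and a drug-effect difference poorly.

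**The case against.** The strongest reply is that this is an exploratory, conditional analysis with no stated decision resting on (d), and that the SAP already offers ways round the gap. Much of that stands:

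- A reader might infer that (d) cannot be derived at all. The documents do not support this. SHAPS curves by group can be computed from a full-dataset model, and a MADRS responder curve is available if the refit is run with lead-in response kept.
- A reader might infer that (d) would show no SHAPS difference. That does not follow either, because baseline score is tested and can separate the groups.
- A reader might infer that the sponsor means to extrapolate the non-responder MADRS model to responders. Nothing in the SAP says so.
- A reader might take protocol 4.2 to say that responders were randomised to test whether the drug works differently in them. It gives wider exposure and an estimate in a broader population, which the protocol's full intention-to-treat analyses supply.
- Observed SHAPS by lead-in group will be visible in the stratified exploratory plots, so (d) is not the only view.
- The sub-population simulations by "simulations will be performed in sub-populations based on specific selection criteria, such as lead-in-placebo-response or baseline SHAPS scores" apply only where judged appropriate, so they are already conditional.
- Sixteen active responders is thin. The SAP's own rule for PK covariates (4.4.3) drops those with fewer than 20 subjects per parameter.

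The reply does not remove the mismatch. The open clause on further covariates sits beside a sentence that specifically excludes this one for SHAPS. Stratified plots of raw data do not change what a model without the term can simulate. An optional MADRS refit does not secure an output listed without condition.

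**Conclusion.** The concern holds as a failure to reconcile SAP 4.7(d) with SAP 4.6. For SHAPS, the requested split comes from a model in which the groups can differ only through other covariates, so similarity between them would be largely assumed. The lead-in observation does not justify that assumption for the treatment weeks. For MADRS, a listed output depends on a discretionary model.

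The effect is limited to the interpretation of one simulation output, and arises only if the exposure-response modelling goes ahead. The responder count rests on the protocol's planning rates. The standard errors also rest on an assumed SHAPS SD of 6 to 8 points. The 4-point difference is a yardstick, not an expected effect. The structural point needs none of these figures. They show that a placebo-course term is worth estimating and that a drug-effect term would be imprecise.

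**What to change.** 1. In SAP 4.6, remove the sentence excluding lead-in response from the SHAPS models. Test it, as a randomisation stratum, at least on the placebo-response parameters of the full-dataset SHAPS model.
2. Treat any lead-in term on the SHAPS drug effect as exploratory and report its estimate with an interval, since only about 16 responders per arm are expected.
3. Make the full-dataset MADRS fit with lead-in response included a precondition for the MADRS part of (d).
4. In SAP 4.7, add that where a scale's model has no lead-in term, (d) is not presented by lead-in response for that scale, or the similarity is labelled as a model assumption.

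The cost is a few lines of SAP text and one or two extra parameters, using data already collected. The downside is slightly less parsimony in an exploratory model. Items 3 and 4 alone would remove the inconsistency. Item 1 lets the SHAPS split be estimated instead of assumed.

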#### 4.7. Simulations

Based on the final PK/PD model (including covariates, if any), model-based simulations of placebo corrected change from baseline in MADRS/SHAPS will be generated. The following simulations will be performed:

- a) Population distribution of the MADRS and SHAPS change from baseline and of the drug effect on MADRS and SHAPS at Week 6 vs AUC;
- b) Probability to achieve a drug effect on MADRS and SHAPS of at least 1, 2, or 3 points drop at Week 6 in the population;
- c) Point estimate and 90% confidence interval (CI) for the MADRS and SHAPS change from baseline and for the drug effect on MADRS and SHAPS at Week 6 vs AUC for the population studied;
- d) Model-based MADRS and SHAPS change from baseline vs time by lead-in placebo-response.

Simulations (a), (b) and (d) will be performed using 10,000 subjects per dose level in order to adequately reflect PK and PD variability in a large population. For this purpose, interindividual variability in PK and in PD parameters, as well as residual variability in MADRS and SHAPS, will be included in the simulations. Uncertainty of model parameter estimates will not be included. Simulations will be performed at the 10 mg qd dose level. Other dosing regimen may be included if deemed appropriate. The simulations will be summarized as median, 5th and 95th percentiles of the population. Simulations (a), (b) and (c) may be repeated for additional treatment days of

interest. When appropriate, simulations will be performed in sub-populations based on specific selection criteria, such as lead-in-placebo-response or baseline SHAPS scores.

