6. **MADRS and SHAPS PK/PD Modelling:** The change from baseline MADRS and SHAPS total score will be modelled separately using specific parameters for placebo effect, and drug effect, using individual JNJ-67953964 exposure estimates in the drug effect sub-model. Baseline scores, co-medication, gender, race and age at baseline will be tested as potential covariates. Primary analysis on MADRS will be performed on the enriched population (lead-in non-responders). In case no effect on MADRS is found, change from baseline SHAPS total scores will be analyzed on the full dataset. If appropriate, the analysis on MADRS may be repeated on the full dataset, where both lead-in placebo response as well as baseline SHAPS total score will be tested as covariate in the model;
7. **Simulations of change in MADRS and SHAPS:** Based on the final PK/PD model (including covariates, if any), model based simulations of the drug effect on MADRS and SHAPS change from baseline (i.e. net MADRS/SHAPS change from baseline after correction for placebo response) will be generated;

8. **Exploration of Exposure versus Safety Parameters:** Exploratory bar plots of AE grade versus exposure quantiles will be generated for the AE's of interest: pruritis and GI complaints. Other AE's with one or more observations of grade 3 or higher may be included in the exploratory analysis as well. If appropriate, a logistic regression may be used to describe the relationship between exposure and the occurrence of an AE.
9. **Reporting:** Prepare the report in accordance with the FDA and EU guidance on population PK.

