#### 4.6. MADRS and SHAPS PK/PD Modelling

Exploratory plots of individual  $AUC_{0-24h}$  versus MADRS and SHAPS total score, both absolute and change from baseline, stratified by lead-in placebo-response and by visit will be created. The exposure-response analysis will only be performed for the efficacy endpoints if the exploratory analysis shows a relationship in exposure-efficacy.

The MADRS and SHAPS total score data will be modelled using specific parameters for baseline response, placebo effect, and drug effect, according to the following general equation:

$$y_{ij} = (\theta_1 v_1 + \theta_2 v_2 + \theta_3 v_3 + \theta_4 v_4 + \theta_5 v_5 + \alpha_i) + f_i(v_j, C_i) + \varepsilon_{ij}$$

where  $y_{ij}$  represents the change from baseline MADRS or SHAPS total score for the  $i$ -th subject at the  $j$ -th time point ( $j=1..5$  for the 5 post-baseline visits in Week 1, 3, 4, 5 and 6),  $\theta_{1-5}$  represent the fixed effects for the placebo response at the post-baseline visits, i.e.  $j=1..5$  (with  $v_{1-5}$  denoting indicator variables with value 1 when  $j$  is equal to Treatment Week 1, 3, 4, 5 and 6),  $\alpha_i$  represents the random effect parameter for non-drug-related response,  $f_i(v_j, C_i)$  representing the concentration-effect relationship for JNJ-67953964 in the  $i$ -th subject at the post-baseline visits, i.e.  $j=1..5$  as a function of the exposure metric  $C_i$ , and  $\varepsilon_{ij}$  represents the residual variability associated to measurement  $y_{ij}$ . Baseline is defined as treatment baseline, i.e. last observation before the first dose.

The inter-individual variability (IIV) random effect  $\alpha_i$ , and any random effect within  $f_i$  will be assumed to be normally-distributed, zero-mean, uncorrelated random variables. The residual variability random effects  $\varepsilon_{ij}$  will be assumed to be normally-distributed, zero mean, uncorrelated random variables that are also uncorrelated with respect to  $\alpha_i$ , and any random effect within  $f_i$ . Alternative distributions for the IIV and the residual variability random effects may be considered if needed. If warranted by the data, parametric functions of time (e.g. linear, exponential) may be used to describe the placebo effect.

The exposure metrics to be used in the PK/PD model will be  $AUC_{24h}$  (see Section 4.5). Additional exposure metrics may be tested if the  $R^2$  of the correlation between PK parameters is less than 0.8.

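### Simulation (b), the probability of a 1-, 2- or 3-point drug effect, does not say whether residual score noise enters the thresholded quantity, and it carries no margin for parameter uncertainty

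*SAP*

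**What the plan says.** SAP 4.7 lists four outputs. Output (b) is the "Probability to achieve a drug effect on MADRS and SHAPS of at least 1, 2, or 3 points drop at Week 6 in the population". The settings follow in one block: "Simulations (a), (b) and (d) will be performed using 10,000 subjects per dose level", between-subject variability in PK and PD parameters "as well as residual variability in MADRS and SHAPS, will be included in the simulations", and "Uncertainty of model parameter estimates will not be included". No sentence treats (b) differently from (a) or (d).

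Output (c) is separate and also refers to Week 6: "Point estimate and 90% confidence interval (CI) for the MADRS and SHAPS change from baseline and for the drug effect on MADRS and SHAPS".

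The SAP describes the drug effect in two ways. Step 7 of SAP 4.2 explains it as "net MADRS/SHAPS change from baseline after correction for placebo response", and the opening of 4.7 likewise speaks of a placebo-corrected change. SAP 4.6 instead makes it a separate model term, f_i, "representing the concentration-effect relationship for JNJ-67953964 in the" individual subject, and attaches the residual term ε_ij to the measured score.

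**The concern.** A probability of reaching a threshold depends on what is compared with the threshold and on which sources of variation are allowed to move it. Residual error belongs in a simulation of observed scores. It does not belong in a statement about how many subjects have a drug effect of a given size, because zero-mean noise alone carries many subjects past a small threshold. The thresholds here, 1 to 3 points, are small against a MADRS change SD of 11.

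The second point stands apart from the first. Simulating 10,000 subjects makes Monte Carlo error negligible. Without parameter uncertainty, (b) would then be a precise-looking percentage that rests entirely on the point estimate of a drug effect from a modest trial. A reader of the report could take it as far better known than it is.

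**Working it through.** **Inputs.** From Protocol 9.1: SD of MADRS change 11, effect size 0.45 (0.45 × 11 = 4.95 points), 1-sided alpha 0.20, power 90%, 45 per group. From SAP Table 3: between-subject variability 28.6% on CL/F and 26.3% on F. From SAP 4.9.1: standard error preferably below 50% of the estimate. The documents give no residual SD for MADRS and no SD at all for SHAPS.

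**The plan's own figure.** The SAP states no value for (b), so the figure to reproduce is the sample size that rests on the same SD: n = 2(0.8416 + 1.2816)²/0.45² = 44.5, so 45 per group, with power 0.902. The protocol's figure holds.

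**Problem 1: residual inside the thresholded quantity.** With true drop d and zero-mean normal noise of SD s, P(drop ≥ t) = Φ((d − t)/s). The residual SD is varied because it is not given. SD 11 is the total SD of change, so it is an upper bound for a single residual draw.

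| Noise SD | Share of variance 121 | d = 0: 1, 2, 3 points |
|---|---|---|
| 3.48 | 10% | 38.7%, 28.3%, 19.4% |
| 4.92 | 20% | 41.9%, 34.2%, 27.1% |
| 7 (assumed) | 40% | 44%, 39%, 33% |
| 7.78 | 50% | 44.9%, 39.9%, 35.0% |
| 11 | 100% | 46.4%, 42.8%, 39.3% |

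The 1-point figure passes 40% when Φ(−1/s) > 0.40, that is s > 1/0.2533 = 3.95, or about 13% of 121 (3.95² = 15.6). With d = 4.95 and s = 11, the 1-point figure is Φ(3.95/11) = 64%. At that noise level the output separates no effect from the planned effect only as 46% against 64%.

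Adding parameter uncertainty while the residual stays in barely moves this. With SE 2.32, s becomes √(121 + 2.32²) = 11.24, and the 1-point figure goes from 46.4% to 46.5%.

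If (b) thresholds f_i alone, a fitted effect of zero gives 0% at every threshold.

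**Problem 2: f_i alone, estimate treated as exact.** Approximate SE of the Week 6 difference: 11 × √(2/45) = 2.32. A model that just meets the preferred 50% relative SE then has an effect of 2 × 2.32 = 4.64 points. Assume an effect linear in AUC, with no further random effect on it, and lognormal AUC with CV √(0.286² + 0.263²) = 0.39 and mean 1. On the log scale the SD is √ln(1 + 0.39²) ≈ 0.375, and the share of subjects reaching 3 points at mean effect m is Φ((ln(m/3) − 0.375²/2)/0.375).

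- m = 4.64: about 84%.
- Lower 90% limit, 4.64 − 1.645 × 2.32 = 0.82: about 0%.
- Upper 90% limit, 4.64 + 1.645 × 2.32 = 8.46: over 99%.

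**The case against.** The strongest reply is that the SAP already separates scores from drug effect. The model equation in SAP 4.6 puts the residual on the measurement and the drug effect in f_i. Outputs (a) and (c) name change from baseline and drug effect as two things, while (b) names only the drug effect. The residual variability is described as being in MADRS and SHAPS, that is, in scores. On this reading problem 1 is not in the plan. The reading is reasonable and may be the intended one. It is still not stated, and the net-change description in 4.2 together with the shared setting in 4.7 lets a programmer do otherwise.

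On problem 2, the reply is that the SAP discloses that (b) is conditional on the fitted model, and that (c) shows estimation uncertainty separately. Both are true, and without residual error (b) is a valid description of population spread given the estimates. But the interval in (c) is for the effect. It does not say how far the percentage in (b) could move.

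The gates also matter. Modelling and simulation proceed only if exploratory plots suggest a relationship, and SAP 4.9.1 sets significance and precision criteria. A drug with no true effect would reach (b) only with a non-zero fitted effect, so the zero-effect rows above illustrate the noise and do not predict a reported result. The gates limit how imprecise the model can be, which is why problem 2 is worked at the 50% limit. They do not remove the uncertainty there.

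**Conclusion.** The point holds as two separate, modest defects. The SAP leaves open whether (b) contains residual error, and on either reading (b) carries no margin for parameter uncertainty. If the residual is included, a zero effect on MADRS shows more than 40% at 1 point for any noise SD above 3.95 (44% at an assumed SD of 7, 46% at the upper bound of 11). If f_i alone is used, the example at the preferred precision limit gives 84% at 3 points, with a range from 0% to over 99%. That example assumes a linear effect, AUC CV of 39%, and a two-group, single-visit SE rather than the SE of the repeated-measures exposure model. The size for SHAPS cannot be checked.

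A reader might infer more than the documents support:

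- That an ineffective drug will be reported as reaching 1 point in over 40% of subjects. This needs the residual inside the thresholded quantity; with f_i alone and a fitted effect of zero it is 0%.
- That leaving out parameter uncertainty causes the 40%. It does not; the residual alone does.
- That (b) is a go/no-go figure. SAP section 2 frames the exposure-efficacy work as exploratory, and Protocol 9.2.1 places the primary comparison in the MMRM contrast at 6 weeks.

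**What to change.** In SAP 4.7, state that (b) compares f_i from the drug-effect sub-model, without residual error, with the 1-, 2- and 3-point thresholds. Repeat (b) over parameter sets drawn from the estimation covariance matrix or a bootstrap, and report each probability with a 90% interval. Keep residual error in (a) and (d) where observed scores are simulated.

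The cost is a short text change and some computing time. The reported probability will come with a visibly wider interval. No new data and no change in trial conduct are needed.
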